## **12.0 CRITERIA FOR THERAPEUTIC RESPONSE/OUTCOME ASSESSMENT**

### **12.1 Assessment of Primary Objectives**

12.1.1 Assessment of the overall toxicity rate will occur at the pre-specified follow-up time-points using the CTCAE version 4.0 grading system. The radiation oncologist will score toxicity at each visit. Any toxicity recorded within three months of completion of radiation will be considered acute. Any toxicity after three months from completion of radiation will be considered late toxicity.

### **12.2 Assessment of Secondary Objectives**

### **12.2.1 Assessment of Pulmonary Failure-Free Survival**

A CT scan of the chest will be obtained at 3 and 6 months (+/- 3 weeks) and at 12, 18, and 24 months (+/- 6 weeks) post-treatment. This study will use a modified Response Evaluation Criteria in Solid Tumor (RECIST) for assessment of tumor response. The baseline scan will be the pre-irradiation CT scan.

All patients will be assessed as failure or failure free as defined below. Pulmonary failure-free survival will be defined as survival with no progressive disease in the lungs. CR, PR, and SD will be considered failure-free.

For patients with measurable ( $\geq 5\text{mm}$  but  $<10\text{mm}$ ) lung lesions at the time of study entry:

- a. The investigator will identify up to 5 measurable lung lesions to be followed for response. The sum of the longest diameter (LD) for all target lesions will be calculated and reported as the disease measurement.
- b. Complete response (CR) is defined as the disappearance of all target lesions.
- c. Partial response (PR) is defined as at least a 30% decrease in the disease measurement, taking as reference the pre-irradiation CT scan.
- d. Progressive disease (PD) is defined as at least a 20% increase in the disease measurement, taking as reference the smallest disease measurement recorded since start of treatment, or the appearance of one or more new lung lesions.
- e. Stable disease (SD) is neither sufficient shrinkage to qualify for PR nor sufficient increase to qualify for PD.

For patients with no measurable disease present at baseline:

- a. Stable disease (SD) is defined as no appearance of measurable lesions in the treated area
- b. Progressive disease (PD) is defined as the appearance of measurable lesions on post-treatment scans and will be considered failure-free if no measurable lesions develop.

**12.2.2 Assessment of overall survival** will be performed for each patient using clinical data and information from the social security database.

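### Section 12.2.1 states no failure rule for growth of non-target lung lesions, and counts new nodules under 5 mm as failure in only one baseline group

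*Combined protocol and SAP*

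**What the plan says.** Protocol section 12.2.1 gives one parent definition for everyone: "Pulmonary failure-free survival will be defined as survival with no progressive disease in the lungs". It then says "All patients will be assessed as failure or failure free as defined below" and "CR, PR, and SD will be considered failure-free". The only outside reference is this: "This study will use a modified Response Evaluation Criteria in Solid Tumor (RECIST) for assessment of tumor response". No RECIST version is named.

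Two rule sets follow.

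- **Patients with "measurable ( $\geq 5\text{mm}$ but $<10\text{mm}$ ) lung lesions at the time of study entry".** "The investigator will identify up to 5 measurable lung lesions to be followed for response". The disease measurement is the sum of the longest diameters of those targets. Item (d) makes progression either a rise of 20% or more over the smallest sum recorded since treatment began, or any new lesion in the lung, with no minimum size. Complete and partial response are also judged on the targets alone, and stable disease is whatever remains.
- **Patients with no measurable disease at baseline.** "Progressive disease (PD) is defined as the appearance of measurable lesions on post-treatment scans". The matching line for stability reads "Stable disease (SD) is defined as no appearance of measurable lesions in the treated area".

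Neither rule set mentions non-target lesions. The inclusion criteria (6.2) set no upper limit on the number of lung metastases. Section 14.0 makes pulmonary failure the event of interest in a cumulative incidence analysis, with other progressions and death as competing risks. It adds nothing to the definition of failure.

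**The concern.** A lung lesion that was visible at baseline but not chosen as a target is outside the sum, and it is not new. Under the written rules its growth cannot make the patient a failure, however large it becomes. That contradicts the parent definition, which asks for no progression in the lungs and not merely in the targets. A patient does not need six lesions for this to arise: one target plus one nodule under 5 mm is enough.

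The new-lesion rules also differ between the groups. One has no size floor and the other requires a measurable lesion, so a very small new nodule is an event for some patients and not for others.

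At stake is the meaning of the study's only lung-control endpoint. The non-target gap misses or delays failures. The missing size floor adds events in one group only. The pooled rate then depends partly on the mix of baseline disease. Section 14.0 does not help: an analyst who sees clear non-target growth could follow 12.2.1 and ignore it, or could code it as a competing progression.

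**Working it through.** **Figure to reproduce.** There is none. The plan states no rate, power or sample size for this endpoint, and the probability table in section 14.0 concerns only the 1-year toxicity rule. The check is to apply the 12.2.1 rules literally to test lesions. The lesion sizes below are illustrations, not figures from the plan.

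**Inputs.** Up to 5 targets, sum of longest diameters, 20% threshold, new-lesion route (12.2.1, measurable group); measurable range of 5 mm to under 10 mm (12.2.1); measurable lesions required for progression (12.2.1, no-measurable group); 15 patients (14.0); endpoint evaluated only in patients who complete radiation and have at least one follow-up chest CT (13.0).

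**Step 1: growth of a non-target lesion, measurable group.** Progression requires current sum ≥ 1.2 × smallest sum, or a new lung lesion.

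- Five stable 6 mm targets: sum 5 × 6 = 30 mm before and after, change 30/30 − 1 = 0%. A sixth baseline lesion grows from 8 to 30 mm. It is not in the sum and not new, so the result is stable disease, failure-free. If it were counted, the sum would go from 38 to 60 mm: 60/38 − 1 = +58%.
- One stable 7 mm target and a baseline nodule growing from 4 to 9 mm: change in sum 0%, so failure-free. By contrast, the target alone growing from 7 to 8.4 mm gives 8.4/7 = 1.2, which is progression. Growth of 1.4 mm in the target is failure; growth of 5 mm in the nodule beside it is not.

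**Step 2: a new nodule, by baseline group** (in the first group, with stable targets).

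| New nodule | Measurable lesions at baseline | No measurable disease at baseline |
|---|---|---|
| 2, 3 or 4 mm | Progression | Not progression |
| 5 to 9 mm | Progression | Progression |
| 10 mm or more | Progression | Progression if only the 5 mm floor applies; not if the upper bound of the range is taken literally |

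The clear disagreement is below 5 mm. The last row reflects a separate wording problem: the range stops below 10 mm, although 6.2 admits lesions up to 2 cm.

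**Step 3: weight of one patient.** Change in the crude failure proportion = 1/n.

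- n = 15: 1/15 = 6.7 percentage points.
- n = 13 (assumed): 1/13 = 7.7 points.
- n = 10 (assumed): 1/10 = 10.0 points.

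Section 13.0 means n can be at most 15, so 6.7 points is the minimum. This is a crude proportion; the planned estimator is a cumulative incidence function.

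**The case against.** The strongest reply is that the plan invokes a modified RECIST, so a non-target rule may carry over without being written out. The documents cannot exclude that intention. They also do not supply the rule: no version is named, the criteria are modified, and patients are to be classified by the definitions given in the section. The safe statement is that no rule is stated and that the written rules lead to failure-free.

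Three further points stand.

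- Misclassification needs an untracked lesion to grow while the target sum stays below +20% and no new lung lesion appears. With five scheduled CTs, a later scan may trigger failure anyway, so the error may be a delay.
- Having separate rules for the two groups is not in itself an error. Requiring measurable size where nothing is being tracked is defensible, though it does not explain why the other group has no floor.
- The endpoint is secondary and nothing is decided on it.

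Some stronger readings are tempting, but the documents do not support them.

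- A reader might infer that failure is judged over different anatomical regions in the two groups. The reference to the treated area is only in the stability line, "Stable disease (SD) is defined as no appearance of measurable lesions in the treated area". The progression line for that group carries no location, and the parent definition says the lungs for everyone.
- A reader might infer that any new nodule is treated differently by group. From 5 to 9 mm it is failure in both.
- A reader might infer that a 4 mm baseline nodule growing to measurable size is certainly failure when there is no measurable disease at baseline. That is a natural reading, but a lesion already visible does not strictly appear, so the contrast is possible rather than certain.
- A reader might put a number on the patients affected, because 6.2 sets no cap and section 3.2 describes diffuse lung involvement. Neither gives a count. The remark in 3.2 concerns relapse after resection, which may show as new lesions and so already count in the measurable group.

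**Conclusion.** The point holds in two parts. First, in patients with measurable lesions, the written rules classify growth of a non-target baseline lung lesion as failure-free, against the endpoint's own parent definition. This is a wrong classification under the text, not only missing detail. Second, a new nodule under 5 mm is failure in one baseline group and not in the other.

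Each patient reclassified moves the crude failure proportion by at least 6.7 percentage points. How many would be affected is unknown, and because the two parts push in opposite directions, the net bias in the pooled rate cannot be stated. The conclusion assumes that the rules listed in 12.2.1 are complete, as the section itself indicates. The 1-year toxicity decision rule in section 14.0 is unaffected. The wording should be corrected, but the primary conclusion of the study does not depend on it.

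**What to change.** Amend 12.2.1 in three places.

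1. Add to item (d) a third route: *or unequivocal progression of a non-target lung lesion, including a baseline nodule under 5 mm that grows to 5 mm or more*.
2. Apply one size threshold to new lesions in both groups: 5 mm or more, with no upper limit. Stating the size directly avoids relying on the present measurable range, which stops below 10 mm and does not fit the 2 cm entry limit in 6.2.
3. Use the lungs, as in the parent definition, as the region in both rule sets. A radiotherapy target volume should not be substituted: the clinical target volume in 9.2.3 includes the pleural recesses and hila, and could widen the endpoint beyond the parent definition.

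If a particular RECIST non-target rule was intended, name the version and state the rule instead of the clause in item 1.

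The change is to wording only, with no extra scans or readers. It has two costs: judging unequivocal progression brings in some investigator judgement, and a new nodule under 5 mm is counted only when it reaches 5 mm, possibly one scan later.

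### Pulmonary progression is a 20% rise over the nadir with no minimum absolute growth, so a single 5-9 mm lesion fails on 1.0-1.8 mm and a stable patient can be counted as a failure

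*Combined protocol and SAP*

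**What the plan says.** Section 12.2.1 of the protocol adopts its own version of RECIST: "This study will use a modified Response Evaluation Criteria in Solid Tumor (RECIST) for assessment of tumor response". The pre-irradiation CT is the baseline. Measurable lesions are those from 5 mm to just under 10 mm. "The investigator will identify up to 5 measurable lung lesions to be followed for response", and "The sum of the longest diameter (LD) for all target lesions will be calculated and reported as the disease measurement". The sum can therefore consist of one lesion.

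Under item (d), progression is "at least a 20% increase in the disease measurement, taking as reference the smallest disease measurement recorded since start of treatment". Item (d) also offers a second route, with no size stated: "or the appearance of one or more new lung lesions". Progression is failure; complete response, partial response and stable disease are failure-free.

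Patients with no measurable lesion at baseline follow another rule: "Progressive disease (PD) is defined as the appearance of measurable lesions on post-treatment scans".

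The scan schedule supplies up to five comparisons: "A CT scan of the chest will be obtained at 3 and 6 months (+/- 3 weeks) and at 12, 18, and 24 months". Section 14.0 analyses the endpoint by cumulative incidence, with pulmonary failure as the event, in a study of 15 patients. Section 13.0 limits the analysis to patients who complete radiation and have at least one follow-up chest CT.

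The documents give no minimum absolute increase, confirmatory scan, independent read or allowance for measurement error.

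**The concern.** A purely relative threshold shrinks with the lesion. At the bottom of the size range it is 1 mm, the same as the step between two readings recorded in whole millimetres. Two features add to this. The reference is the smallest earlier value, so a low reading by chance lowers the bar for every later scan. The comparison is also repeated at up to five scans, with no provision to confirm or reverse a call.

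Any resulting error goes one way: stable patients become failures and lung control looks worse than it is. There is no comparator arm to share the bias. With at most 15 patients, one false failure moves the crude failure proportion by at least 1/15 = 6.7 percentage points.

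**Working it through.** The plan states no error rate or precision for this endpoint, so there is no figure to reproduce.

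**Inputs from Section 12.2.1:** 20% threshold; nadir reference; lesions from 5 mm to under 10 mm; one to five target lesions; five post-treatment scans. **Assumption:** the SD of a single diameter reading, taken as 0.25 to 1.0 mm because the documents give none.

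**Step 1: growth that triggers failure, one lesion.** Threshold = 0.20 x reference.
- 5 mm: 0.20 x 5 = 1.0 mm
- 7 mm: 0.20 x 7 = 1.4 mm
- 9 mm: 0.20 x 9 = 1.8 mm
- after shrinkage to 4 or 3 mm: 0.8 or 0.6 mm

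With five 5 mm lesions the sum is 25 mm and the threshold is 5.0 mm.

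**Step 2: one follow-up scan, stable lesion.** Let each reading be X = m + e, with e normal, SD s, independent between scans. Failure is X1 >= 1.2 X0, so P = 1 - Phi(0.2m / (s x sqrt(1 + 1.2^2))). For m = 5 mm and s = 0.5 mm this is 1 - Phi(1.0 / (0.5 x 1.562)) = 1 - Phi(1.28) = 0.10. For s = 1.0 mm it is 1 - Phi(0.64) = 0.26.

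**Step 3: repeated scans.** Failure is any scan at or above 1.2 times the running minimum, with the pre-irradiation scan counted in the minimum. Simulated probability of failure with no true change, unrounded readings:

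| SD (mm) | one 5 mm, 5 scans | one 7 mm, 5 scans | one 9 mm, 5 scans | one 5 mm, 3 scans | five 5 mm, 5 scans |
|---|---|---|---|---|---|
| 0.25 | 0.06 | 0.002 | 0.00 | 0.03 | 0.00 |
| 0.5 | 0.61 | 0.31 | 0.11 | 0.37 | 0.03 |
| 0.75 | 0.84 | 0.66 | 0.45 | 0.61 | 0.25 |
| 1.0 | 0.92 | 0.82 | 0.69 | 0.72 | 0.51 |

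Variants:
- Rounding to whole millimetres raises the single 5 mm figure over five scans to 0.21 at SD 0.25 mm, 0.83 at 0.5 mm and 0.97 at 1.0 mm.
- Leaving the pre-irradiation scan out of the nadir lowers the unrounded figures at SD 0.5 mm to 0.50, 0.23 and 0.08 for 5, 7 and 9 mm.
- Two 5 mm lesions, rounded, give 0.54 at SD 0.5 mm and 0.88 at 1.0 mm.

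**Step 4: effect of an absolute minimum.** One stable lesion, five scans, unrounded, requiring both conditions:

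| SD (mm) | 20% only, 5 mm lesion | 20% and 3 mm | 20% and 5 mm |
|---|---|---|---|
| 0.5 | 0.61 | 0.00 | 0.00 |
| 0.75 | 0.84 | 0.03 | 0.00 |
| 1.0 | 0.92 | 0.17 | 0.003 |

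**Step 5: delay in calling true growth.** A 5 mm lesion growing linearly, read without error, is called at the first scheduled scan that meets the rule:

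| Growth (mm/year) | 20% only | 20% and 3 mm | 20% and 5 mm |
|---|---|---|---|
| 2 | 6 months | 18 months | not by 24 months (reaches 9 mm) |
| 3 | 6 months | 12 months | 24 months |
| 4 | 3 months | 12 months | 18 months |
| 5 | 3 months | 12 months | 12 months |

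**The case against.** The strongest objection is that the size of the problem is not in the documents. It rests on an assumed measurement error, and at SD 0.25 mm the unrounded risk is 0.06 for a 5 mm lesion and practically nil at 7-9 mm. The highest figures need one lesion, the smallest size, rounded readings and all five scans. Section 14.0 expects 50% of patients to die within a year, so many will not have five scans. Section 4.2 admits patients with no residual lung disease, who are outside the 20% rule, and the number with one or two small lesions is not stated. All of this stands. It limits what can be claimed about frequency but leaves the gap in the definition. Fewer scans reduce the risk without removing it: 0.37 over three scans for a 5 mm lesion at SD 0.5 mm.

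A reader might infer that the two baseline groups fail at very different amounts of growth. The text does not support that in general. A patient without measurable disease may have a nodule under 5 mm, and growth from 4 to 5 mm is failure after 1 mm, the same as for a single 5 mm target lesion.

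A reader might also infer that the protocol's 5 mm limit supplies the missing growth margin. It does not. It is a minimum size for calling a lesion measurable, and says nothing about how much a sum of one to five diameters must grow.

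Finally, an absolute minimum has a cost: it delays or misses slow true progression, which would flatter the treatment. That is a real trade-off and a reason to report both definitions.

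**Conclusion.** The gap is real. As written, the rule fails a single 5-9 mm lesion on 1.0-1.8 mm of growth over the nadir, and nothing elsewhere in the documents closes it. A truly stable patient can be counted as a pulmonary failure. For one stable lesion over five scans the probability runs from about 0 (9 mm, SD 0.25 mm) to about 0.92 (5 mm, SD 1.0 mm), unrounded. With five 5 mm target lesions it is 0.03 at SD 0.5 mm and becomes large only as the SD approaches 1 mm.

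It would go too far to say that stable patients will be counted as failures, or to put a number on the bias in the trial's result. That needs the measurement error and the mix of lesion counts and sizes, and the documents give neither. The figures also assume independent errors between scans and attendance at every scan counted.

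The scope is one of two secondary objectives, with no comparator, hypothesis or decision rule attached. The primary safety decision in Section 14.0 is unaffected.

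**What to change.** In Section 12.2.1(d), define progression on target lesions as a rise of at least 20% and of at least a stated number of millimetres in the sum over the nadir, or a new lesion. Choose the minimum from the measurement error expected for CT diameters at this institution, and state that error. Because the error of a sum of k independent readings grows as SD x sqrt(k), check the choice for more than one lesion: with two stable 5 mm lesions and rounded readings, a 5 mm minimum still leaves up to 0.15 at SD 1.0 mm. State also whether the pre-irradiation scan counts towards the nadir.

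Report the 20%-only definition as a sensitivity analysis, so that the effect of the minimum is visible in both directions.

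The cost is one phrase and one extra tabulation, with no additional scans. The downside is later recognition of slow growth. With a 5 mm minimum, a 5 mm lesion growing 3-4 mm a year is called three scheduled scans later, and one growing 2 mm a year is not called within 24 months. A 3 mm minimum delays these by one or two scans, but leaves more false failures (up to 0.17 at SD 1.0 mm). The change concerns only how the endpoint is counted, not how patients are managed.

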## 1.0 PROTOCOL SUMMARY AND/OR SCHEMA

This is a safety study to evaluate toxicity and other clinical outcomes of whole lung intensity-modulated radiation therapy (IMRT) following standard treatment in patients with synovial sarcoma and lung metastases. Patients who received standard therapy for synovial sarcoma will be assessed for residual disease in the lungs by post-therapy imaging. Patients with pulmonary metastases  $\leq 2$  cm will then be eligible to receive Whole Lung Irradiation (WLI). The treatment plan will involve 1500 cGy of radiation delivered using IMRT in 150 cGy fractions.

Following completion of treatment, patients will have CT chest, physical exams, and toxicity assessments at 3, 6, 12, 18, and 24 months (+/-3 weeks for 3 and 6 months and +/-6 weeks for 12, 18, and 24 months), an echocardiogram at 6, 12, and 24 months, and pulmonary function tests at 6 and 24 months.

Fifteen patients will be enrolled in 6 years. The duration of the study will be 6 years.

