## **4.1 OVERVIEW OF STUDY DESIGN/INTERVENTION**

### **4.2 Design**

This is a single institution study involving patients with synovial sarcoma who have completed all standard therapy (e.g. surgery +/- radiation to the primary site) +/- any adjuvant chemotherapy. The sequence and types of therapy offered prior to WLI will likely vary based on primary tumor site, tumor resectability, extent of metastatic disease, performance status, and comorbidity. Each patient's therapy will be determined by the disease management team irrespective of participation on this protocol.

Patients are eligible for this protocol if their pulmonary metastases are present at diagnosis or develop over the course of treatment. After completion of all planned therapy, patients will be assessed with a CT scan of their lungs and a PET scan if the CT scan shows residual lung metastases. Assuming there is no residual pulmonary disease or that any remaining pulmonary metastases are  $\leq 2$  cm, patients will proceed to WLI. If there is gross disease in the lung  $>2$  cm, patients will be evaluated for metastasectomy. If they undergo metastasectomy and subsequently have no residual pulmonary disease or have pulmonary metastases  $\leq 2$  cm, they are eligible to receive WLI on this protocol. Patients will also have an echocardiogram and pulmonary function tests (PFTs) prior to initiation of whole lung irradiation to assess baseline cardiac and pulmonary function. Patients will be simulated for external beam radiation with the use of a 4D CT to account for respiratory motion, as per standard practice. Patients will be treated with IMRT to 1500cGy in 150cGy fractions.

After completion of WLI, patients will be followed by members of the Radiation Oncology department for toxicity evaluations and will be evaluated by physical exams and chest CT scans at 3, 6, 12, 18, and 24 months (+/-3-6 weeks depending on timepoint). Patients will also have echocardiograms at 6 months (+/- 3 weeks) and 12, and 24 months (+/- 6 weeks). Patients will also undergo pulmonary function tests (PFTs) at 6 months (+/- 3 weeks) and 24 months (+/- 6 weeks). Any severe toxicity due to radiation will be carefully evaluated and further accrual will be terminated if the level of toxicity is greater than expected. The protocol may be terminated or modified as determined by the principal investigator. Please see section 11.0 regarding specific dose limiting toxicities and stopping rules for the protocol.

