### **6.1 CRITERIA FOR SUBJECT ELIGIBILITY**

## 6.2 Subject Inclusion Criteria

- Patients with synovial sarcoma confirmed by MSKCC pathological review
- Patients with single or multiple lung metastases at diagnosis or that develop over the course of treatment.
- After completion of all chemotherapy, lung metastases must be  $\leq 2$  cm.
- Age  $\geq 12$  months of age
- Karnofsky performance status (KPS) must be  $\geq 70$  for patients  $\geq 16$  years of age and Lansky performance status must be  $\geq 70$  for patients  $< 16$  years of age.
- Normal cardiac function
  - No active coronary artery disease;
  - No New York Heart Association class II, III or IV disease;
  - No arrhythmia requiring treatment.
  - Baseline echocardiogram with a shortening fraction of  $\geq 27\%$  or an ejection fraction  $\geq 50\%$ .
- Female patients of childbearing potential must have a negative pregnancy test within 14 days of radiation start.
- Female patients who are lactating must agree to stop breast-feeding.
- Sexually active patients of childbearing potential must agree to use effective contraception.

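### Measurable lung lesions are bounded at 5 to under 10 mm although metastases up to 2 cm are eligible, so read literally a sole 10 to 20 mm lesion has no growth rule for progression, and the follow-up threshold is unclear

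*Combined protocol and SAP*

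**What the plan says.** Section 12.2.1 sorts patients into two groups. The first is introduced with the only size definition of measurable in the document: "For patients with measurable ( $\geq 5\text{mm}$ but $<10\text{mm}$ ) lung lesions at the time of study entry". In this group up to five measurable lesions are followed. Progressive disease (PD) is a rise of at least 20% in the summed diameters from the smallest value recorded, or any new lung lesion.

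The second group has no measurable disease at baseline. Its stable disease (SD) rule is "Stable disease (SD) is defined as no appearance of measurable lesions in the treated area", and its PD rule is "Progressive disease (PD) is defined as the appearance of measurable lesions on post-treatment scans and will be considered failure-free if no measurable lesions develop". Neither mentions growth of a lesion that was already there.

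The endpoint is then built on these categories: "Pulmonary failure-free survival will be defined as survival with no progressive disease in the lungs", and "CR, PR, and SD will be considered failure-free". The section describes its criteria as a modified RECIST but gives no version and does not list the modifications.

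Eligibility uses a different size limit. Section 6.2 states "After completion of all chemotherapy, lung metastases must be" 2 cm or smaller. Section 4.2 has the same limit ("Assuming there is no residual pulmonary disease or that any remaining pulmonary metastases are" within 2 cm), and Section 1.0 repeats it. Section 14.0 analyses pulmonary failure by cumulative incidence, with other progressions and death as competing risks.

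**The concern.** The upper bound of 10 mm on measurable disease sits inside the eligible range, which runs to 20 mm. The largest lesions the protocol admits therefore fall outside the only group that has a growth criterion. A literal reader would place a patient with nothing but 10 to 20 mm lesions among those without measurable disease, and could record progression only if some further lesion appeared.

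At stake is the first-listed secondary objective, and the only endpoint that describes control in the lung. If growth of such a lesion is scored as SD and the patient then dies, the Section 14.0 analysis counts a competing death where a pulmonary failure occurred. That path is realistic: Section 14.0 expects 50% of patients to have died without grade 3 toxicity by 1 year. A second problem is that readers cannot tell what size makes a lesion measurable on a post-treatment scan.

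**Working it through.** The question is one of definition, and the plan states no figure to reproduce. The check applies the Section 12.2.1 rules to example lesions within the 20 mm entry limit, first literally (measurable means 5 mm or more and under 10 mm) and then with the lower bound only (5 mm or more). The lesion sizes are illustrations.

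**Inputs.** Bounds of 5 and 10 mm, a 20% growth rule and at most five targets (Section 12.2.1); entry limit of 20 mm (Sections 1.0, 4.2, 6.2); 15 patients and 10% withdrawal within 1 year (Section 14.0).

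**Classification**

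| Baseline to follow-up | Change | Literal rule | Lower bound only |
|---|---|---|---|
| 8 mm to 9.6 mm | 9.6/8 = 1.20, +20% | PD | PD |
| 15 mm to 18 mm | 18/15 = 1.20, +20% | SD, failure-free | PD |
| 15 mm to 30 mm | 30/15 = 2.00, +100% | SD, failure-free | PD |
| 8 and 15 mm to 8 and 30 mm | targets 8 to 8, 0%; both lesions 23 to 38, 38/23 = 1.65, +65% | SD, if the entry bounds govern target choice | PD |
| none to a new 7 mm lesion | new | PD, if the same bounds apply at follow-up | PD |
| none to a new 12 mm lesion | new | not PD, if the same bounds apply at follow-up | PD |

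1. *Sole lesion of 10 to 20 mm.* It is not measurable at entry, so the second group's rules apply. Growth of a lesion already on the baseline CT is not an appearance, so the result is SD at any size. The patient can still fail if a new qualifying lesion develops.
2. *Mixed sizes.* Targets must be chosen at baseline, because partial response is measured against the pre-irradiation CT. If the entry bounds govern that choice, the 15 mm lesion is excluded whatever is assumed about follow-up scans. It could be a target only if the bounds are taken to define the patient group and not the targets.
3. *Follow-up scans.* If the same bounds apply, a new 7 mm lesion is a failure in the second group and a new 12 mm lesion is not. If the bounds apply at entry only, no size is given for follow-up.

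**Size of effect.** Without censoring, cumulative incidence is failures divided by N. With 5 failures assumed, 5/15 = 33.3%. If one is missed and ends as a competing death, 4/15 = 26.7%. The difference is 1/15 = 6.7 points, whatever number of failures is assumed. Withdrawal of 10% is 0.10 × 15 = 1.5 patients. If 1 or 2 leave before any event, the step is 1/14 = 7.1 or 1/13 = 7.7 points. Section 13.0 restricts this endpoint to patients who complete radiation and have a follow-up CT, without giving a number; if 10 were evaluable (an assumption), the step is 1/10 = 10 points.

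If a qualifying new lesion appears on a later scan, the failure is recorded late: the curve is too low in between and not at the end.

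**The case against.** The strongest reply is that Section 12.2.1 adopts a modified RECIST. The bracketed range could be that modification, extending measurability downward, with larger lesions left to the parent standard; or text covering larger lesions may have been left out. A sensible reader might then treat a 15 mm lesion as a target. This stands to the extent that the literal reading is not the only possible one. It does not close the gap: no version or list of modifications is given, so the documents neither confirm nor exclude it, and readers would have to override a written upper bound.

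It is also fair that the endpoint is secondary, has no decision rule, and that a missed growth event often changes only the timing.

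A reader might infer more than the text supports:

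- *That shrinkage could be scored as failure*, for example 12 mm falling to 8 mm and so entering the measurable range. A lesion visible at baseline has not appeared when it shrinks, so this reading is strained and no weight is put on it.
- *That 10 to 20 mm lesions are expected*, because a baseline PET is planned. Sections 8.1 and 10.0 plan PET for any metastasis below or up to 2 cm, including those under 10 mm, and Section 4.2 also admits patients with no residual disease. Such lesions are permitted; their frequency is not given.
- *That the plan counts PD as failure-free*, from the run-on wording of item b. The section elsewhere limits failure-free status to CR, PR and SD, so this is an editorial fault.

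**Conclusion.** The point holds for a secondary endpoint. The written bounds conflict with the eligibility limit, and followed literally they classify doubling of an eligible lesion as failure-free while a 1.6 mm increase in an 8 mm lesion (9.6 − 8) is progression. The follow-up threshold is unclear on any reading.

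The likely direction is missed or late pulmonary failures. The total bias cannot be computed, because the mix of lesion sizes is not given. The 6.7 points per missed failure assumes 15 evaluable patients, no censoring, and no qualifying new lesion on any later scan. Under the Section 12.2.1 definition, which requires survival, a patient who dies is no longer failure-free; there the error for that patient is one of timing.

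A reader might infer that the safety conclusion is in doubt. It is not: the 1-year toxicity decision, the sample size of 15 and the power table in Section 14.0 do not use lesion measurements.

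**What to change.** In Section 12.2.1:

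- Define measurable, at baseline and on follow-up scans, as a longest diameter of at least 5 mm with no upper bound.
- Make all such baseline lesions eligible as targets, up to the five allowed.
- For patients with no measurable disease at baseline, define PD as any lung lesion reaching at least 5 mm on a post-treatment scan, whether new or grown from a baseline lesion under 5 mm. Removing the upper bound alone would leave the second case unclear.
- State how growth of baseline lesions that are not targets is classified, since these also have no rule.
- Split item b into two sentences, one defining PD and one saying who is failure-free.
- Apply the definition to every patient's scans, including any already read.

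The cost is a change of wording, using the same CT schedule. If scans have already been read, their 10 to 20 mm lesions would need to be measured. No sample size or power figure changes.
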